**Table 3-2 Treatment Period and Safety Follow-up Visit Assessments – Study VX15-809-114**

Event/Assessment	Day 1	Week 12	Week 24	Week 36	Week 48	Safety Follow-up Week 52 a
Clinic visit	X	X	X	X	X	X
Vital signs b	X	X	X	X	X	X
Physical examination c					X	X d
Liver Function Testing e	X	X	X	X	X	X
Urine pregnancy test (all female subjects of childbearing potential)	X	X	X	X	X	X
Randomization f	X					
Standardized education on adherence	X					
Concomitant medications, treatments, and procedures	X	X	X	X	X	X
Smart Adherence Technology-Reported Adherence g		X	X	X	X	

LUM/IVA drug count i		X	X	X	X	
Ophthalmologic examination j					X	
AEs and SAEs	Continuous from signing of ICF or assent (where applicable)					
LUM/IVA resupply	Every 3 months throughout study					

AE: adverse event; ICF: informed consent form; IVA: ivacaftor; IWRS: interactive web response system; LUM: lumacaftor; PE: physical examination; SAE: serious adverse event; [REDACTED]

a The Safety Follow-up Visit is 28 ( $\pm$  7) days after the last dose of LUM/IVA (Section 8.1.3).

b Vital signs will be assessed following a 5-minute rest in the seated or supine position.

c Symptom-targeted PEs will occur at any time during the study if triggered by AEs or if deemed necessary by the investigator.

d Required for subjects who do not begin commercial LUM/IVA after Week 48 only.

e Day 1 only blood draws will be collected before the first dose of LUM/IVA. Liver function testing (alanine aminotransferase [ALT], aspartate aminotransferase [AST], gamma-glutamyl transpeptidase [GGT], alkaline phosphatase [ALP], and total bilirubin) must be performed at the scheduled visits (Section 11.5.2).

f Randomization must occur after all inclusion and exclusion criteria are met and before the first dose of LUM/IVA. Randomization will be done through IWRS.

g Data will be collected for all subjects throughout the study in real-time. Subjects in Study Arm A will review data with physicians at study visits.

i LUM/IVA drug count will be collected at the end of specified study visits.

j See Section 11.5.6.

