### 8.1.4 Early Termination of Treatment

Subjects who prematurely discontinue LUM/IVA treatment for any reason (except withdrawal of consent or assent) and who do not begin commercial LUM/IVA will be asked to return to the clinical site 28 ( $\pm$  7) days of their last dose of LUM/IVA for a Safety Follow-up Visit.

Assessments performed at this visit will be the same for those in the Safety Follow-up Visit ([Table 3-2](#)).

If the subject withdraws consent or assent for the study, no further evaluations should be performed and no additional data should be collected. Vertex may retain and continue to use any data collected before such withdrawal of consent.

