### **9.4 Removal of Subjects**

Subjects may withdraw from the study at any time at their own request and subjects may be withdrawn at any time at the discretion of the treating physician or by Vertex for safety, behavior, noncompliance with study procedures, or administrative reasons. LUM/IVA treatment will be withdrawn for any female subject who has confirmed pregnancy and for any male subject whose female partner has a confirmed pregnancy. A subject may be withdrawn from the LUM/IVA treatment after a discussion between the investigator and the medical monitor for any of the following reasons:

- A subject develops a medical condition that requires prolonged concomitant therapy with a prohibited medication or prolonged interruption of LUM/IVA combination therapy.
- A subject develops a life-threatening adverse event or a serious adverse event (SAE) that places him/her at immediate risk, and discontinuation of treatment with LUM/IVA and withdrawal from the study are deemed necessary
- A subject is noncompliant with the study requirements
- A subject has an increase in transaminases (ALT or AST), meeting criteria for interruption of LUM/IVA in Section 11.5.3.

A subject should be discontinued from the study for the following reason:

A subject on a transplant list undergoes lung transplantation

If a subject does not return for a scheduled visit, reasonable effort will be made to contact the subject. In any circumstance, reasonable effort will be made to document subject outcome. The investigator will inquire about the reason for withdrawal, request that the subject return all unused LUM/IVA, request that the subject return for a Safety Follow-up Visit, if applicable (see Section 8.1.4), and follow up with the subject regarding any unresolved AEs.

If the subject withdraws consent for the study, no further evaluations will be performed and no additional data will be collected. Vertex may retain and continue to use any data collected before such withdrawal of consent.

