#### Smart Pill Bottles

Subjects will be trained to use the smart pill bottle. Subjects in Study Arm A will receive additional instruction on the activated smart pill bottle monitoring features. A site pharmacist will repackage 3 months supply of LUM/IVA from blister packs into 4 Smart Pill Bottles. Three bottles will each store a 1-month supply of LUM/IVA. A fourth bottle will store an additional 7 days supply of LUM/IVA. Only 1 bottle will be activated at a time.

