8.2.6 Study Drug Compliance

Study drug compliance based on number of tablets will be assessed by calculating the percentage of tablets consumed relative to the expected number of tablets administered during the subject's actual time on-study. The expected number of tablets administered during the subject's actual time on-study will be 4 tablets per day multiply the number of days in the study. The number of tablets consumed is the difference between the expected number of tablets dispensed and the total number of tablets returned.

These pharmacy and subject reported compliance data will be summarized during the overall treatment duration (from first dose to last dose), based on the medication interruption days.

Compliance rate based on the interruption days will be calculated as follow:

$$100 \times [1 - (\text{total number of days of any study drug interruption}) / (\text{duration of study drug exposure})]$$

The total number of days study drug interrupted is defined as the total of number of days the study drug was interrupted in each interruption interval, where number of days study drug interrupted in each interval is defined as the interruption end date - the corresponding interruption start date + 1.

Study drug compliance will be summarized descriptively by the number of subjects (n), mean, SD, median, min, and max. They will also be summarized in categories: $<80\%$ and $\geq 80\%$ using frequency tables.

Study drug compliance summaries will be based on the FAS.

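### SAP 8.2.6 scores every unreturned tablet as taken and divides by days in the study rather than exposure days, so pill-count compliance is wrong when returns are incomplete

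*SAP*

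**What the plan says.** SAP 8.2.6 gives the pill-count numerator: "The number of tablets consumed is the difference between the expected number of tablets dispensed and the total number of tablets returned". The denominator "will be 4 tablets per day multiply the number of days in the study". Compliance is then described by n, mean, SD, median, minimum and maximum. "They will also be summarized in categories", below 80% and 80% or above. The same section defines a second rate from interruption days, which divides by duration of exposure, and says that the pharmacy and subject data are summarised "based on the medication interruption days".

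Protocol 12.3.2.4 has its own pill-count formula: tablets taken over 4 times the duration of exposure in days. It allows either the pill-count method or the interruption-day method, or both, depending on data availability.

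On supply and return:
- Protocol 10.1.2 dispenses three 1-month bottles together. In addition, "A fourth bottle will store an additional 7 days supply of LUM/IVA".
- Table 3-2 marks the drug count at Weeks 12, 24, 36 and 48 and leaves the Safety Follow-up cell blank. Its footnote reads: "LUM/IVA drug count will be collected at the end of specified study visits".
- Protocol 8.1.4, on the early-termination visit: "Assessments performed at this visit will be the same for those in the Safety Follow-up Visit". Under 8.1.3, subjects who start commercial drug before that visit need not attend it.
- Protocol 9.4 has the investigator "request that the subject return all unused LUM/IVA".
- Protocol 10.9 has subjects told to return all used and unused materials, the site record dispensed and returned amounts, and the monitor review the inventory.

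SAP 8.1 says that missing data are not imputed unless specified. It does not say whether an unreturned bottle is a missing value or a return of zero.

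**The concern.** A dispensed-minus-returned count measures intake only if everything left over comes back and is counted. The SAP formula has no term for tablets that are lost, kept or never counted, so each one raises compliance. It also starts from expected rather than recorded dispensing, although 10.9 requires the actual amounts to be logged.

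Leftover stock is built into the design, because each resupply carries a 7-day reserve. A subject who leaves between counts can hold much of a 3-month supply, and the visit on that route has no count scheduled. SAP Section 3 says that the study was terminated early, so exits between counts are plausible.

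At stake is the protocol's complementary look at adherence alongside the smart-bottle data. An inflated count can move a subject across the 80% line and can give values that are impossible as intake. The denominator adds a separate error: time on study without drug would pull the figure down.

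**Working it through.** The documents report no pill-count result, so there is no stated figure to reproduce. The check applies the SAP formula to simple cases.

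**Inputs**
- 4 tablets per day (SAP 8.2.6; protocol Table 10-1).
- Three 1-month bottles plus 7 days per dispensing (protocol 10.1.2).
- Assumption: a month is 28 to 30 days. One dispensing is then 3 × 28 + 7 = 91 days to 3 × 30 + 7 = 97 days, or 91 × 4 = 364 to 97 × 4 = 388 tablets.
- Reserve bottle: 7 × 4 = 28 tablets.
- Assumption: days in the study means either exposure days alone or exposure plus the nominal 28 follow-up days. The SAP does not say which.

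**Formula:** compliance = 100 × (dispensed − returned) / (4 × days).

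**Case 1: one reserve bottle not returned, 84 exposure days**
- Expected tablets: 84 × 4 = 336. Taken: 252. True compliance: 252/336 = 75%.
- With 364 dispensed, 364 − 252 = 112 are left. The subject returns 112 − 28 = 84, and the formula gives 364 − 84 = 280.
- With 388 dispensed, 136 are left and 108 are returned. The formula again gives 280, so month length does not matter.
- Reported compliance: 280/336 = 83.3%, a shift of 28/336 = 8.3 points. Any subject with true compliance from about 71.7% (80 − 8.3) to just under 80% would be moved into the upper category.
- If the lapse happens once in 24 weeks (168 × 4 = 672 expected tablets), the shift is 28/672 = 4.2 points.

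**Case 2: a fully adherent subject who stops at Day 28**

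Taken: 28 × 4 = 112, leaving 252 (of 364) or 276 (of 388). The denominator is 112 on exposure days, or 56 × 4 = 224 with follow-up days.

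| Leftover tablets returned | Scored as taken | Exposure days | Exposure + 28 days |
|---|---|---|---|
| All | 112 | 100% | 50% |
| Half (126 or 138) | 238 to 250 | 213% to 223% | 106% to 112% |
| None, entered as zero | 364 to 388 | 325% to 346% | 163% to 173% |

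The last row is the same whatever the subject actually took, because intake no longer enters the calculation. The first row shows that early stopping alone does no harm on exposure days, and that the wider denominator halves a correct figure.

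**The case against.** Four points on the other side have weight.

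**Returns are covered elsewhere.** Sections 9.4 and 10.9 have return requested, instructed, logged and inventoried, so a count can exist for an early leaver without a mark in Table 3-2. This stands. A reader might infer that anyone who stops early gets an inflated figure; the documents do not support that, since a full return gives the right answer on exposure days. But a request and a log do not make a return complete, and the SAP has no rule for when it is not.

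**The no-imputation rule may remove the worst case.** The 325% to 346% value needs an absent return entered as zero, which the SAP does not prescribe, and exposure days as denominator. It is a conditional illustration, not an expected result, and it would be visible in the reported maximum. A partial return still yields a number, and an 83.3% would not stand out.

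**Pill count is not the only compliance measure.** The interruption-day rate sits beside it, and the text is unclear on which rate the categories apply to. It does say that tablet-based compliance will be assessed, and the categorical summary does not exclude it.

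**The consequences are limited.** SAP 8.3.2 bases the adherence endpoints on bottle openings, and Section 3 leaves only descriptive summaries. A reader might also infer that disengaged subjects will score highest because they return least. That is a reasonable expectation, but nothing in the documents establishes it.

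**Conclusion.** The point holds for incomplete returns. Followed exactly, SAP 8.2.6 overstates the tablets taken whenever dispensed tablets are not returned or counted. The firmest figure is the 8.3-point shift over 84 exposure days from one full reserve bottle, enough to take a true 75% to 83.3%. It depends only on that bottle being left out of an otherwise complete return. The Day 28 figures depend on the assumed month length, on how an absent return is recorded, and on the meaning of days in the study.

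The denominator is a second defect. It differs from protocol 12.3.2.4 and from the interruption-day rate in the same SAP section. If follow-up days count, it biases the figure downward, so the net direction for an early leaver is not fixed.

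The documents do not support extending this to the adherence endpoints or to the between-arm result on bottle data. It is a correction to a descriptive, supportive summary.

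**What to change.** Amend SAP 8.2.6 as follows:
1. Use the recorded amounts dispensed and returned from the protocol 10.9 accountability log, not expected dispensing.
2. Do not treat unreturned tablets as consumed. Compute pill-count compliance only over dispensing intervals in which all dispensed bottles were returned and counted.
3. Set other intervals to missing, and report the number missing by arm.
4. Use exposure days, first to last dose, as denominator, as in protocol 12.3.2.4.

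This takes SAP wording and records that the protocol already requires. The cost is some missing values, and the summary will describe only subjects and intervals with complete returns. That selection could itself matter and should be stated with the table.

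Adding a drug count to Table 3-2 and 8.1.4 is not worth pursuing here. The study has been terminated, so it could not recover past counts, and subjects who moved to commercial drug would have needed a new contact.

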### **10.4 Dose Modification for Toxicity**

If any unacceptable toxicity arises, a dose modification to LUM 200 mg/IVA 125 mg q12h for up to 7 days may be permitted after discussion with and approval by the medical monitor. Subjects who receive the LUM/IVA dose modification will be administered 1 tablet in the morning and 1 tablet in the afternoon and follow administration instructions as described in Section 10.2.

The medical monitor should be contacted before transitioning subjects back to LUM 400 mg/IVA 250 mg q12h.

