#### LUM/IVA Interruption

LUM/IVA administration must be interrupted immediately and the medical monitor must be notified if any of the following criteria is met:

- ALT or AST  $>5 \times$  ULN
- ALT or AST  $>3 \times$  ULN, in association with total bilirubin  $>2 \times$  ULN

A thorough investigation of potential causes should be conducted and the subject should be followed closely for clinical progression.

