#### **12.3.2.4    Study Drug Exposure and Compliance**

Exposure to LUM/IVA (i.e., duration of treatment in days) will be summarized for the FAS in terms of duration of treatment a subject received (in days), defined as the last day minus the first day of LUM/IVA plus 1. Exposure will be summarized by study arms for the FAS.

Primary and secondary analyses of adherence will be performed through smart technology generated data. A complementary analysis based on pill count and missing/interruption of dose

will be conducted. Information on number of pills and drug interruption will be collected from dispensing pharmacy and subjects.

These pharmacy and subject reported compliance data will be summarized for the FAS and will be derived in at least 1 of 2 methods pending data availability:

(1) based on pill counts calculated as:

$$100 \times (\text{total number of tablets taken}) / (4 \times \text{duration of LUM/IVA exposure in days})$$

And/or:

(2) based on medication interruption days using the formula:

$$100 \times [1 - (\text{total number of days LUM/IVA interrupted} \geq 72) / (\text{duration of LUM/IVA exposure})]$$

Duration of treatment and dosing compliance will be summarized by means of descriptive summary statistics.

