8.2.5 Study Drug Exposure

Exposure summaries will be based on the FAS and presented by treatment group.

Duration of study drug exposure is defined as follows: last dose date – first dose date + 1 day within the treatment period, regardless of any interruption in dosing between the first and the last dose.

If the last dose date of study drug is missing, the subject's discontinuation or completion date will be used for analysis purposes.

Exposure will be summarized as a continuous variable in weeks, and also in the following categories: ≤ 6 weeks, >6 and ≤ 12 weeks; >12 and ≤ 24 weeks; >24 and ≤ 36 weeks; >36 and ≤ 48 weeks; and >48 weeks, for each treatment group.

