8.3.2 Analysis of Adherence Endpoints

Mean percentage adherence to LUM/IVA treatment over treatment duration for all subjects

The percentage adherence over treatment duration for each subject is defined as:

$$100 \times (\text{total number of smart bottle openings over the eligible treatment duration excluding the physician-directed interruption periods of the eligible treatment duration}) / [2 \times (\text{eligible duration of treatment} - \text{the number of physician-directed interruption days of the eligible treatment duration})]$$

Note: (1) the physician-directed interruption is defined as the reported interruptions due to reasons not being “Non-compliance”; (2) if there are more than 2 smart bottle openings at any day, they will be counted as 2 in calculation of the adherence endpoints. (3) the eligible treatment duration = eligible date of last dose – date of first dose + 1, where the eligible date of last dose is defined to be either the CRF collected date of last dose or the last activity date of smart bottle data, whichever is earlier.

Descriptive statistics will be provided by the number of subjects (n), mean, SD, SE, median, min, and max by treatment arm based on FAS. [REDACTED]

The percentage adherence will also be listed.

Mean percentage adherence to LUM/IVA treatment over 0 through 12 weeks for subjects who have at least 12 weeks of eligible smart pill bottle data

Subjects who have at least 12 weeks of eligible smart pill bottle data are defined as those who have at least 12 weeks of eligible treatment duration = eligible date of last dose – date of first dose + 1, where the eligible date of last dose is defined to be either the CRF collected date of last dose or the last activity date of smart bottle data, whichever is earlier.

The percentage adherence over 12 weeks for each eligible subject is defined as:

$$100 \times (\text{total number of smart bottle openings over the first 12 weeks excluding the physician-directed interruption periods of the first 12 weeks}) / [2 \times (12 \text{ weeks (ie, 84 days)} - \text{the number of physician-directed interruption days of the first 12 weeks})]$$

Note: (1) the physician-directed interruption is defined as the reported interruptions due to reasons not being “Non-compliance”; (2) if there are more than 2 smart bottle openings at any day, they will be counted as 2 in calculation of the adherence endpoints.

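### SAP 8.2.6 counts directed interruption days as non-compliance, so a mandated stop of more than 20% of exposure is tabulated as below 80%, while SAP 8.3.2 removes the same days

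*SAP*

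**What the plan says.** SAP 8.2.6 defines two compliance rates. The first is 100 × [1 − interruption days / duration of exposure], where the interruption days are the "total number of days of any study drug interruption". Duration comes from SAP 8.2.5: last dose date minus first dose date plus 1, "regardless of any interruption in dosing between the first and the last dose". The second is tablets consumed over tablets expected. The expected number "will be 4 tablets per day multiply the number of days in the study", and tablets consumed are "the difference between the expected number of tablets dispensed and the total number of tablets returned". Compliance is summarised descriptively and in two categories, below 80% and 80% or more.

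SAP 8.3.2 treats interruptions differently for bottle-based adherence. Openings are counted "excluding the physician-directed interruption periods of the eligible treatment duration", and the same days come off the denominator. Physician-directed there means any reported interruption whose reason is not Non-compliance.

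The protocol itself directs some of these departures from full dosing. Section 11.5.3 states: "LUM/IVA administration must be interrupted immediately and the medical monitor must be notified if any of the following criteria is met". Resumption waits for transaminase recovery and medical monitor approval, so no length is fixed. Section 10.4 allows an approved reduction of up to 7 days: "Subjects who receive the LUM/IVA dose modification will be administered 1 tablet in the morning and 1 tablet in the afternoon".

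Protocol 12.3.2.4 has its own versions of the two rates, introduced by "A complementary analysis based on pill count and missing/interruption of dose". Its interruption formula counts only interruptions of at least 72 (unit not printed there; hours in the endpoint list). Neither protocol formula exempts directed stops.

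**The concern.** The two SAP sections apply opposite rules to the same days. Under 8.3.2 a directed stop is neutral. Under 8.2.6 it scores as failure to comply, and the 80% split can then place a subject who followed every instruction in the lower category. That cut equals one of the thresholds used for the bottle-based proportions, so readers are likely to set the two tables side by side.

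Short exposure makes the problem plausible. The study was terminated early, two of the SAP 8.2.5 exposure categories lie at or below 12 weeks, and three of the four remaining adherence endpoints cover the first 12 weeks. With a short denominator, a stop of a few weeks can cross the cut. At stake is what the compliance table means: it would mix management of tolerability with dosing behaviour under one label.

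**Working it through.** SAP 8.2.6 gives formulas and a cut-off but no worked figure, so there is no plan figure to reproduce. The check applies the formulas to a subject who takes every directed dose.

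**Inputs.** E = days of exposure (SAP 8.2.5). k = days of directed interruption followed by resumption; the documents give no value, so every k below is an assumption. Full dose is 4 tablets per day (SAP 8.2.6). Reduced dose is 2 tablets per day for at most 7 days (Protocol 10.4). The cut-off is 80% (SAP 8.2.6).

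**Interruption-day rate.** 100 × (1 − k/E) is below 80% exactly when k/E exceeds 0.20.

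| E (days) | 0.20 × E | Smallest k giving <80% | Rate at that k | Rate one day shorter |
|---|---|---|---|---|
| 42 | 8.4 | 9 | 78.6% | 81.0% |
| 84 | 16.8 | 17 | 79.8% | 81.0% |
| 168 | 33.6 | 34 | 79.8% | 80.4% |
| 336 | 67.2 | 68 | 79.8% | 80.1% |

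The same stop weighs less as exposure grows. An assumed 28-day stop gives 1 − 28/84 = 66.7%, 1 − 28/168 = 83.3% and 1 − 28/336 = 91.7%.

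**Tablet rate.** 100 × 4(E − k)/(4E) = 100 × (1 − k/E), the same values. This needs two conditions: every unused tablet is returned, and days in the study equal days of exposure. The SAP does not state either.

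**Same subject under SAP 8.3.2.** Take E = 84 and k = 21. SAP 8.2.6 gives 1 − 21/84 = 75.0% for interruption days and 252/336 = 75.0% for tablets. SAP 8.3.2 expects 2 × (84 − 21) = 126 openings. With two openings on each remaining day, the result is 126/126 = 100%.

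**Dose reduction.** One full 7-day reduction removes 7 × 2 = 14 tablets. At 84 days the tablet rate is 322/336 = 95.8%, a loss of 4.2 points. It falls below 80% only if 14/(4E) exceeds 0.20, that is E < 17.5: at 17 days 54/68 = 79.4%, at 18 days 58/72 = 80.6%. A reduction does not enter the interruption-day rate.

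**Change from protocol to SAP.** Reading the protocol's 72 as hours, three 2-day interruptions in 84 days leave its rate at 100%. The SAP formula gives 1 − 6/84 = 92.9%.

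**The case against.** The strongest reply is that 8.2.6 is a simple, disclosed summary inherited from the protocol. Protocol 12.3.2.4 already expects 4 tablets per day of exposure and has no exemption for directed stops, so the SAP did not create the gap. The section sits under background characteristics, feeds no endpoint or test, and only descriptive summaries remain after early termination. All of this stands, and it limits the weight of the point. It does not remove the inconsistency: the SAP itself widened the protocol's formula to any interruption, and it exempts directed days in 8.3.2 but not in 8.2.6.

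Several stronger readings are tempting, and the documents do not support them.

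- **An approved dose reduction makes a subject non-compliant.** One reduction cannot do so at 12 weeks; it needs 17 or fewer days in the study.
- **Every tablet not taken counts against the subject.** Consumption is dispensed minus returned, so an untaken tablet that is not returned counts as consumed.
- **Any mandated stop lowers the rate.** A permanent stop does not lower the interruption-day rate, because exposure ends at the last dose.
- **The compliance table is a failed check on the device.** The protocol calls the analysis complementary. Neither document assigns these rates the task of validating the bottle or plans a comparison of the two tables.

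**Conclusion.** The point holds as an internal inconsistency with a conditional consequence. A subject who follows every instruction is classed below 80% by the interruption-day rate when a directed, temporary stop exceeds 20% of exposure. The tablet rate agrees under the two conditions given above. It would go too far to say that full compliers with a safety stop are generally reported as non-compliers: this depends on stop lengths, which the documents do not give, and longer exposure makes it progressively less likely. The dose-reduction part is a small downward bias in the tablet rate, not a reclassification at realistic exposures. The damage is confined to the descriptive compliance tables, and the adherence endpoints in SAP 8.3.2 are unaffected. The change is worth making because it is cheap and the study's subject is adherence.

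**What to change.** Amend SAP 8.2.6 so that both rates are relative to what was directed. Let P be physician-directed interruption days, identified by the interruption reason used in 8.3.2, N the other interruption days, and R the days on an approved reduced dose.

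- **Interruption-day rate:** 100 × [1 − N/(E − P)].
- **Tablet rate:** take P out of the expected count. Where dated dose-reduction records exist, set expected tablets on those days to the number directed, giving 4 × (E − P − R) + 2 × R.

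In the examples above, the 21-day stop then gives 1 − 0/63 = 100% and 252/252 = 100%. The 7-day reduction gives 322/(4 × 77 + 2 × 7) = 322/322 = 100%.

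If the all-interruption figure is still wanted, report it alongside under a label other than compliance and without the 80% split.

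The cost is a small derivation change, and the figures will differ from the protocol's simple formula. There are two dependencies. The fix inherits the 8.3.2 rule that any reason other than Non-compliance is physician-directed, which may exempt stops that no physician ordered. The dose-reduction step needs dated records: the protocol shows a dose-reduced category for adverse event action (Table 13-3) but describes no daily-dose record.
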